10.1.1 Screening Procedures, Enrollment and Randomization

The screening and enrollment flowchart for randomization is presented in **Figure 4**. Patients identified by or presented to the trial site with aortic stenosis will be screened by the site team for the inclusion and exclusion criteria described in 9.3 and 9.4, using available medical records, including relevant imaging studies previously performed for diagnostic purposes. If the patient is deemed a potential candidate for the trial, all aspects of the trial will be explained to the patient. The patient will then be invited to participate in the SMART Trial. If the patient agrees to participate, electronic (only applicable to US/Canada per IRB/REB approval) or written informed consent will be obtained. This will be considered the point of enrollment. If the local Heart Team considers the subject suitable for implantation, the subject's clinical information will be submitted to Medtronic via completion of the Screening Visit eCRFs and image transfer. Each subject will undergo a Confirmation of Qualification process (i.e., screening process) to review the subject's anatomical characteristics and verify eligibility criteria.

The following assessments must be completed within 12 weeks prior to submission for Confirmation of Qualification, unless otherwise indicated:

- Clinical assessment and medical history
 - Physical examination including height, weight, systolic and diastolic blood pressure, and body surface area.
 - NYHA classification
- Heart Team eligibility assessment
- STS-PROM Score
- Syntax Score to confirm exclusion criterion not met
 - Note that a diagnostic coronary angiogram to determine Syntax score will not be required if the subject has no history of coronary artery disease or prior coronary intervention
- MDCT angiogram, with contrast within 365 days prior to submission
- Transthoracic Echocardiogram (TTE)

[figure not shown]

Figure 4. Screening, Enrollment and Randomization Flowchart

[figure not shown]
*Note: Timing of local Heart Team decision can differ from this flowchart but should always occur before a subject is submitted for Confirmation of Qualification

Subjects should give informed consent before undergoing any protocol-required testing. However, if any of the protocol-required baseline/screening evaluations (e.g., echocardiography and MDCT) have been performed for clinical diagnostic purposes prior to consenting, they can be used as the protocol-required exams, provided they were obtained within the protocol-required time windows and contain the necessary information.

All sites will be required to maintain the Subject Identification & Enrollment Log to record the subjects screened for the trial meeting general inclusion criteria who have signed the approved Informed

Version 4.0, 15-Dec-2021

Page 34 of 131

Consent document. Further, neither the Medtronic SE TAV nor the Edwards BE TAV will be used as an emergency treatment.

The SMART Trial will include a Confirmation of Qualification process conducted by Medtronic Clinical Analysts and an independent Case Planning Committee to review the anatomical suitability of potential subjects identified by the site for both Medtronic Evolut PRO/PRO+/FX TAV and Edwards SAPIEN 3/3 Ultra TAV. Subjects with questionable anatomical suitability due to exclusion criteria for the trial, warnings, precautions, or contraindications in the Instructions for Use, or risk factors for TAVR implantation per product training will be reviewed and discussed between the site and the independent Case Planning Committee. Questionable anatomical suitability includes valve area out of range, small sinus of Valsalva (SoV), small femoral, low coronary height, severe left ventricular outflow tract (LVOT) calcification, narrow sinotubular junction (STJ), horizontal aorta, and challenging bicuspid morphology. Depending on whether a subject's anatomical suitability meet entry criteria for the trial, a recommendation to proceed with randomization or reevaluate/exit the subject will be provided to the site.

The Confirmation of Qualification process and Case Planning Committee will ensure appropriate and consistent subject selection across all sites. Prior to the onset of the trial, a charter will be developed which outlines roles and responsibilities as well as describe the screening process.

Subjects confirmed eligible for implantation via the Confirmation of Qualification process will be randomized in a 1:1 basis electronically from an Interactive Response Technology (IRT) system to receive transcatheter aortic valve replacement (TAVR) with either a Medtronic SE or an Edwards BE TAV. Randomization will be stratified by site and sex.

Trial randomization will not be blinded to the subject and site investigative team. Once randomization is complete and a treatment arm is assigned, crossover is not permitted. In the event a crossover occurs, a protocol deviation will be reported and the subject should continue to be followed through the duration of the trial. Distribution of the subjects within the trial groups will be controlled at the implanting sites by means of a central randomization system. Implantation should occur within 30 days post randomization. If the TAVR procedure will occur after 30 days, prior approval of Medtronic is not required, however a protocol deviation must be completed.

[figure not shown]
10.1.2 Baseline

The following assessments must be completed within 14 days prior to TAVR index:

- Clinical assessment including physical examination
- Laboratory tests glomerular filtration rate (GFR), hemoglobin, international normalized ratio (INR) for subjects on warfarin, and serum creatinine
- Use of relevant medications including anticoagulants and antiplatelets
- NYHA classification
- Modified Rankin Score (mRS)
- 6 Minute Walk Test (refer to Appendix Section 18.1)
- Quality of Life Questionnaires: EQ-5D and KCCQ
- Adverse Event Review

Version 4.0, 15-Dec-2021

Page 35 of 131

• Syntax score and TTE, to confirm eligibility criteria, if not determined at the Screening Visit (per Section 10.1.1) or prior to submission for Confirmation of Qualification

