10.1.3 Implant Procedure (TAVR)

The implant visit must occur within 30 days after subject randomization. If the TAVR procedure will occur after 30 days, prior approval of Medtronic is not required, however a protocol deviation must be completed. The following information is required to be collected at the implant visit:

- 12-Lead ECG
 - o within 48 hours prior to procedure
 - within 2 hours after the TAVR procedure. Refer to Appendix Section 18.2 Conduction
 Disturbance Management for subjects with pre-existing conduction abnormalities and new conduction disturbance
- Procedural angiogram
- Adverse Event Review

Subject eligibility criteria should be reviewed to confirm inclusion criteria still met and the subject does not meet any of the exclusion criteria prior to the TAVR procedure. Subjects must be treated via percutaneous transfemoral access only. Procedural aspects specific to the Medtronic SE TAV or Edwards BE TAV system should be performed according to the respective Instructions for Use. Concomitant procedures including percutaneous Coronary Intervention (PCI) are not permitted to be completed during the index procedure.

The Medtronic valve deployment should be performed in every case in accordance to the cusp overlap technique via procedural angiogram, unless patient related factors prevent using this procedural technique.

All procedural angiograms will be reviewed by an internal Procedural Oversight Committee of Medtronic physicians using the procedural checklist for both Medtronic SE TAV or Edwards BE TAV system. Procedures (refer to Appendix VI: Procedural Checklists). Those procedures for which there are questions or concerns about the implantation methods will be referred to the Training and Education Committee (TEC) for review.

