10.2 Data Collection

[figure not shown]
Data collection requirements are summarized in **Table 4** below.

Table 4: Data collection and trial procedure requirements at subject visits

Visit/Assessments (for all subjects unless noted otherwise)	Screening	Baseline	TAVR Procedure	Discharge	30 Days	12 Months	2 Years	Annually 3- 5 Years
Timeframe/Window	Within 12 weeks of submission for Confirmation of Qualification, unless noted otherwise	Within 14 days of TAVR Procedure	Day 0; within 30 days post- randomization	Between 24 hours and 7 days post - procedure (or prior to discharge, whichever comes first)	Between 30- and 45-days post implant	Day 365 + 30 days	Implant anniversary date and ± 30 days	Implant anniversary date and ± 60 days
Informed Consent (and Health Insurance Portability and Accountability Act (HIPAA) Authorization in the US)	X							
Demographics,								
Medical History and	X							
Comorbidities								
Inclusion and	Х		X^1					
Exclusion Criteria	^		^					
STS-PROM Score	X							
Heart Team Assessment	Х							
MDCT Angiogram,	X ²							
with contrast	^							
Adverse Event	X	X	Х	X	Х	Х	Х	Х
Review ³	^	^	^	^	^	^	^	^
Clinical Assessment	V	V		V	Х	V	Х	Х
(including Physical Examination)	Х	X		X	X	Х	X	^
NYHA Classification	Х	Х		X	Χ	Х	Х	Х

Version 4.0, 15-Dec-2021

Page 40 of 131

Visit/Assessments (for all subjects unless noted otherwise)	Screening	Baseline	TAVR Procedure	Discharge	30 Days	12 Months	2 Years	Annually 3- 5 Years
Timeframe/Window	Within 12 weeks of submission for Confirmation of Qualification, unless noted otherwise	Within 14 days of TAVR Procedure	Day 0; within 30 days post- randomization	Between 24 hours and 7 days post - procedure (or prior to discharge, whichever comes first)	Between 30- and 45-days post implant	Day 365 + 30 days	Implant anniversary date and ± 30 days	Implant anniversary date and ± 60 days
Transthoracic								
Echocardiogram (TTE)	X			X	Х	Х	X	X
Laboratory tests		Х						
Medications (i.e., anticoagulants and antiplatelets)		х		х	х	Х	Х	х
Modified Rankin Score ⁴		Х						
6 Minute Walk Test		Х			Χ	Х	Х	Х
Quality of Life Questionnaires ⁵		Х			Х	х	х	х
Procedural Angiogram			х					
12-Lead ECG ⁶			X ⁷	Х	Х	Х		
Stress echocardiogram (conducted at select sites)	ovioused prior to the TAVP of					Х		

¹Subject eligibility criteria reviewed prior to the TAVR procedure

² Pre-implant MDCT must be within 365 days prior to submission for Confirmation of Qualification

³ SAEs, non-serious endpoint-related AEs, ADEs and DDs

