Stroke Definitions	 Disabling stroke: an mRS score of 2 or more at 90 days and an increase in at least 1 mRS category from an individual's pre-stroke baseline Non-disabling stroke: an mRS score of <2 at 90 days or one that does not result in an increase in at least 1 mRS category from an individual's pre-stroke baseline
Stroke Classification	 Ischemic: an acute episode of focal cerebral, spinal, or retinal dysfunction caused by infarction of the central nervous system tissue Hemorrhagic: an acute episode of focal or global cerebral or spinal dysfunction caused by intraparenchymal, intraventricular, or subarachnoid hemorrhage
	Undetermined: insufficient information to allow categorization as ischemic or hemorrhagic

Rehospitalization

Rehospitalization is defined as follows: Any admission after the index hospitalization or study enrollment to an inpatient unit or hospital ward for at least 24 hrs (including an emergency department stay), or as measured by a change in calendar date. Hospitalizations planned for pre-existing conditions are excluded unless there is worsening of the baseline condition.

Version 4.0, 15-Dec-2021

Page 106 of 131

Cardiovascular Hospitalizations

Includes hospitalizations for heart failure, stroke or TIA, conduction disturbances and arrhythmias, vascular or access-site related complications, cardiac structural complications, myocardial infarction, unstable angina, cardiogenic shock, or other cardiovascular hospitalizations.

Heart Failure Hospitalization (or rehospitalization)

Definition:

- 1. Admission to the hospital with a primary diagnosis of Heart Failure (HF)
- Documented new or worsening symptoms due to HF on presentation, including at least one of the following: dyspnoea (dyspnoea with exertion, dyspnea at rest, orthopnoea, paroxysmal nocturnal dyspnoea); decreased exercise tolerance; fatigue; or other symptoms of worsened end-organ perfusion or volume overload
- 3. Objective evidence of new or worsening HF, consisting of at least two physical examination findings or one physical examination finding and one laboratory or invasively measured criterion, including:

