Aortic valve re-intervention will be adjudicated by the CEC and analysis will be based on data collected on the CEC adjudication form. The endpoint will be analyzed with Kaplan-Meier survival analysis according to Section 7.2 for each time point. Analysis of the endpoint will use the AT analysis set.

8. 6MWT at 30 days, 12 months and annually to 5 years

The six-minute walk test (6MWT) measures the distance walked in meters (m). Distance walked at each time point will be summarized as a continuous outcome within treatment arm. The number of subjects unable to perform the test will also be tabulated by reason at each visit. Within each arm, change from baseline will be summarized descriptively. Analysis will be performed using the AT analysis set for all subjects able to complete the assessment at the follow-up visit.

9. QoL (KCCQ, EQ-5D) at 30 days, 12 months and annually to 5 years

056-F286, Statistical Analysis Plan Template

Medtronic

Revision 5.0

The Kansas City Cardiomyopathy Questionnaire (KCCQ) is a 23-item self-administered instrument and responses will be collected in the CRF. The domain and summary scores include: Physical Limitation, Symptom Stability, Symptom Frequency, Symptom Burden, Total Symptom Score, Self-efficacy, Quality of Life, Social Limitation, Overall Summary Score, and Clinical Summary Score. At each follow-up time point, the overall summary score and clinical summary score will be summarized descriptively as continuous data within treatment arm. For each treatment arm, change from baseline will be summarized. Analysis will be performed using the AT analysis set.

The EQ-5D Index will be summarized as continuous data within treatment arm at each follow-up timepoint. Additionally, for each treatment arm, change from baseline will be summarized descriptively. Analysis will be performed using the AT analysis set.

10. BVD (HSVD, NSVD, thrombosis, endocarditis, and aortic valve re-intervention) at 2 to 5 years annually

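### KCCQ, EQ-5D, 6MWT and mRS baselines are timed to TAVR and not to randomisation, so they may follow the open allocation, and must do so when TAVR is more than 14 days after it

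*Protocol*

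**What the plan says.** Protocol 10.1.2 lists mRS, 6MWT, EQ-5D and KCCQ among the Baseline assessments under one timing rule: "The following assessments must be completed within 14 days prior to TAVR index". Table 4 in Protocol 10.2 gives the same anchor: "Within 14 days of TAVR Procedure". Neither the Screening list in Protocol 10.1.1 nor the Screening column of Table 4 includes any of the four. NYHA class, by contrast, is collected at both visits.

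Under Protocol 10.1.1, a subject is randomised once Confirmation of Qualification has been passed; completion of the Baseline visit is not a condition. The same section states: "Trial randomization will not be blinded to the subject and site investigative team". On timing of treatment it says "Implantation should occur within 30 days post randomization", and Protocol 10.1.3 repeats the limit: "The implant visit must occur within 30 days after subject randomization". The limit is soft: "If the TAVR procedure will occur after 30 days, prior approval of Medtronic is not required, however a protocol deviation must be completed".

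The SAP does not define baseline relative to randomisation. For 6MWT, SAP 7.9.4 plans: "Within each arm, change from baseline will be summarized descriptively". It plans the same kind of summary for KCCQ and EQ-5D. In Protocol 18.5.1, part of the definition of disabling stroke is "an increase in at least 1 mRS category from an individual's pre-stroke baseline".

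**The concern.** A baseline should be fixed before anyone knows the allocation. Two of these measures are self-reported, one depends on effort, and one is rated by site staff. The bias controls listed in Protocol section 6 (CEC adjudication, echo core laboratory, standard echo acquisition, eligibility screening) do not protect KCCQ, EQ-5D or 6MWT.

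Two things are at stake. First, if knowing the valve moves the baseline in one arm more than in the other, that shift enters any between-arm reading of change, with its sign reversed. The endpoints are introduced as comparisons of the two valve types, so readers will make that comparison. Second, Protocol 14.7 and SAP 7.6 compare baseline variables between arms, including in the ITT set. For these four variables the comparison may no longer describe the arms as randomised. ITT subjects who leave between randomisation and TAVR may also have no value, because the visit is tied to a procedure that never took place.

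**Working it through.** The plan states no figure on this point, so there is none to reproduce. The check is on the windows.

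**Inputs**
- Baseline window: 14 days, counted back from TAVR (Protocol 10.1.2, Table 4).
- Randomisation to TAVR: up to 30 days without a deviation (Protocol 10.1.1, 10.1.3).
- Trial size, used only for scale: 700 as-treated subjects (SAP 6).
- Distribution of the delay: not in the documents, so assumed.

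**Step 1. Position of the window.** Let randomisation be day 0 and TAVR day T. The Baseline window runs from day T - 14 to day T.
- T = 1: day -13 to day 1
- T = 14: day 0 to day 14
- T = 15: day 1 to day 15
- T = 30: day 16 to day 30

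For T up to 14 the baseline may fall on either side of randomisation, and nothing says which. For T of 15 or more the whole window lies after it. The rule that allows earlier clinical examinations to be reused (Protocol 10.1.1, 10.4) does not help, because they must still fall inside the required window.

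**Step 2. Share of permitted days.** Days 15 to 30 are 16 of the 30 permitted days: 16/30 = 53%. Counting day 0 gives 16/31 = 52%. Procedures after day 30 also belong to this group.

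**Step 3. Share of subjects, under assumed delays.**
- Uniform over days 1-30: 53%, about 370 of 700.
- Exponential with mean parameter m, truncated at 30 days: share = (exp(-14/m) - exp(-30/m)) / (1 - exp(-30/m)).
  - m = 14 days: (0.368 - 0.117) / 0.883 = 28%, about 199 of 700
  - m = 10 days: 21%, about 145
  - m = 7 days: 12%, about 86
  - m = 3 days: 1%, about 7

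These count only subjects for whom a post-allocation baseline is unavoidable. Some treated by day 14 may have one too.

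**Step 4. Effect on a change contrast.** The arm difference in change equals the arm difference at follow-up minus the arm difference at baseline. If a share p of one arm has its baseline shifted by d, the contrast moves by -p x d. The documents give no value for d, and zero is possible. For illustration, with d of 2 or 5 points on the 0-100 KCCQ scale and p = 0.533, the movement is 0.533 x 2 = 1.1 or 0.533 x 5 = 2.7 points. With p = 0.12 it is 0.12 x 2 = 0.2 or 0.12 x 5 = 0.6 points. At d = 0 it is nil.

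**The case against.** The case for leaving the plan alone has several parts.

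- **No inference uses these baselines.** SAP 7.9.4 makes the non-powered secondary outcomes descriptive, and change is summarised within arm. This stands.
- **Absolute values are reported as well.** The SAP summarises 6MWT distance, KCCQ summary scores and the EQ-5D index at each follow-up. These do not use the baseline, so a reader could see a divergence between absolute and change results. It would therefore be too strong to infer that a baseline shift cannot be told apart from a device effect.
- **The route to the clinical co-primary endpoint is narrow.** The stroke definition refers to the individual's state before the stroke and does not name the Baseline visit value. It also requires an mRS of 2 or more at 90 days, and the CEC adjudicates. A misrated baseline matters only if it is wrong by a whole category, in a subject who later has a stroke, where that category decides the classification. A reader might infer that the co-primary result is biased; the documents do not support that.
- **Differential expectation is speculative.** Both arms receive a commercially approved valve. Follow-up questionnaires are open-label too, so if knowing the valve shifts answers similarly at both times, subtraction partly cancels it. This stands as a limit on the size and direction of bias. An earlier baseline does not cure open-label follow-up.
- **A window close to treatment keeps the baseline current.** This is a fair aim in symptomatic severe aortic stenosis, and it bears on how the fix is built.
- **Other pre-randomisation data survive.** NYHA class, examination, STS-PROM and echocardiography have Screening timing. They do not replace the four measures at issue.

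Figure 4, the screening and randomisation flowchart, is not visible in the text reviewed. If it places Baseline before randomisation, it would still have to be reconciled with the TAVR-based window.

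**Conclusion.** The timing gap is real and follows from the text alone. Post-allocation baselines are permitted for all subjects, and are the only in-window option for anyone treated more than 14 days after randomisation.

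A reader might go further and infer that most subjects are affected. The documents do not support this: the 53% rests on a uniform delay, shorter delays give about 1% to 28%, and the true share is unknown until the dates are compared. The KCCQ shifts are likewise illustrations with no source in the documents.

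The consequences are limited to descriptive change-from-baseline summaries for KCCQ, EQ-5D and 6MWT, and to baseline comparisons of these variables and mRS. No hypothesis test uses them, and any effect through mRS on disabling stroke is probably small. This is a cheap improvement and not a threat to the primary conclusions.

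**What to change.** In Protocol 10.1.2 and Table 4, require KCCQ, EQ-5D, 6MWT and mRS after consent and before the IRT randomisation call, in a short window before that call. Leave the other Baseline items within 14 days of TAVR.

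The 12-week Screening window should not be used for this. It is counted back from submission for Confirmation of Qualification, so a baseline could be 84 + 30 = 114 days old at TAVR before any review time is added. With a window of w days before the call, the maximum age is w + 30 days if TAVR keeps to its limit. With w = 14, for example, it is 14 + 30 = 44 days.

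For subjects already randomised, add to the SAP:
- a flag for baselines dated after randomisation, with same-day cases marked as undetermined unless clock times are available;
- the share flagged, by arm;
- a repeat of the change-from-baseline summaries in subjects with a pre-randomisation baseline.

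The cost is one visit-schedule amendment and a date comparison in programming, with no new procedure. The downside is that baselines will be older at TAVR, by up to the randomisation-to-TAVR interval (about 30 days) plus the chosen window. The date comparison needs no protocol amendment and would replace the assumed shares with the actual one.

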14.3.2 Randomized Population

If the subject signs informed consent, meets all inclusion and none of the exclusion criteria, and the Heart Team determines the subject is suitable for randomization in the trial, then the subject will undergo a Confirmation for Qualification. If the subject is approved, the subject will be randomized and added to the randomized population. Within the randomized population the following analysis sets are distinguished:

The intention to treat (ITT) set: Subjects are reported according to the randomized assignment, either BE or SE TAV, regardless of what, if any, therapy was actually received.

The as treated (AT) set: The AT set consists of all ITT subjects with an attempted implant procedure, defined as when the subject is brought into the procedure room and any of the following have occurred: anesthesia administered, vascular line placed, TEE placed or any monitoring line placed. Subjects will be analyzed according to their first attempted procedure (BE or SE TAV).

The implanted set: The Implanted set consists of all the AT subjects who are actually implanted with either TAV.

The primary analysis for the non-ECHO related objectives will use the AT analysis set. The primary analysis for the ECHO related objectives (such as BVD) will use the implanted analysis set.

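### Section 10.1.2 lets the echocardiogram and Syntax score that establish eligibility be done after open-label randomisation, against the sections that require eligibility first

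*Protocol*

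**What the plan says.** Five parts of the plan bear on this.

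- **Baseline fallback.** Protocol 10.1.2 opens with "The following assessments must be completed within 14 days prior to TAVR index". Its last item includes "Syntax score and TTE, to confirm eligibility criteria, if not determined at the Screening Visit". The item also requires that the test was not available by the time the subject was put forward for Confirmation of Qualification. The version history lists the TTE wording as an addition in version 4.0, so it is not a leftover.
- **Interval and blinding.** Protocol 10.1.1 states "Implantation should occur within 30 days post randomization". A later procedure is a protocol deviation but needs no prior approval. The same section states "Trial randomization will not be blinded to the subject and site investigative team".
- **Rules that put eligibility first.** Protocol 10.1.1 states "The following assessments must be completed within 12 weeks prior to submission for Confirmation of Qualification, unless otherwise indicated", and both the Syntax score and the TTE are on the list that follows. It then sends only subjects confirmed as eligible to the randomisation system. Protocol section 6 names screening against the criteria ahead of enrolment and randomisation as a measure against bias. Protocol 14.3.2 and SAP 7.1.3.2 have the subject meeting every criterion before Confirmation of Qualification. Before the procedure, Table 4 marks the TTE at Screening and not at Baseline. It has no Syntax row.
- **Review before the procedure.** Protocol 10.1.3 adds "Subject eligibility criteria should be reviewed to confirm inclusion criteria still met".
- **Analysis sets.** Protocol 14.3.2 states "The primary analysis for the non-ECHO related objectives will use the AT analysis set", and gives the echo objectives, including BVD, to the implanted set. The as-treated (AT) set needs an attempted procedure, and the implanted set is a subset of it.

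**The concern.** Randomisation protects the comparison only if the decision on who belongs in the trial is made before the arm is known. Here the two tests that settle I2 and E2 may come later, read at a site that knows which valve was assigned.

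The consequence runs through the analysis sets. A subject who fails I2 or E2 at that stage and is not taken to the procedure remains in the ITT set but is in neither set that decides a co-primary endpoint. If such exits differed between arms in number or in prognosis, the treated groups would no longer be the groups that were randomised.

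The sample size target is counted in treated subjects, so the issue is comparability of the arms and not power.

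**Working it through.** The plan gives no figure for exits between randomisation and procedure. SAP section 5 says only that the randomised total is expected to exceed 700 because not everyone randomised will be implanted. The check is therefore one of timing and of comparing sections.

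**Step 1: where the Baseline window falls.** Inputs are the 14-day Baseline window (10.1.2) and the 30-day limit from randomisation to implant (10.1.1). With randomisation at day 0 and TAVR at day *t*, the window runs from *t* − 14 to *t*.

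| TAVR day *t* | Baseline window | Position relative to randomisation |
|---|---|---|
| 10 | −4 to 10 | straddles it |
| 14 | 0 to 14 | starts on the same day |
| 15 | 1 to 15 | wholly after |
| 30 | 16 to 30 | wholly after |

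For any *t* above 14, an in-window Baseline test must come after randomisation. For smaller *t* it may.

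**Step 2: whom the fallback covers.** By its own condition it applies when the test was done neither at Screening nor before submission. A subject using it has therefore already been submitted for Confirmation of Qualification without that result. At best the test falls between submission and randomisation. At worst it falls after randomisation.

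**Step 3: whether another section closes the gap.** The list in 10.1.1 allows exceptions where otherwise indicated, and 10.1.2 can be read as one. That might reconcile those two sections. It does not reconcile 10.1.2 with section 6, with the rule in 10.1.1 that only confirmed-eligible subjects are randomised, or with 14.3.2. Confirmation of Qualification is said to verify eligibility, but it cannot verify a result that does not yet exist.

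**Step 4: what happens to a subject who then fails.** No attempted procedure means not in AT, and so not in the implanted set. For the clinical composite, SAP 7.9.1 plans an ITT sensitivity analysis. A second one, by assigned arm, is limited to attempted implants and so omits these subjects again. Scheduled follow-up is set out for treated subjects (Protocol 10.1.5) and Kaplan-Meier time points count from implant (SAP 7.2), so untreated subjects would add little to the ITT analysis. For BVD, the supportive analyses listed in SAP 7.9.2 use the implanted population, and none is by ITT.

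**Step 5: whether a bias can be sized.** Let *p* be an arm's event rate among all randomised, *x* the fraction lost in this way and *r* the event risk of those lost. The rate in those remaining is (*p* − *x r*)/(1 − *x*), a shift of *x*(*p* − *r*)/(1 − *x*). The sign depends on whether *r* is above or below *p*, and the effect on the comparison depends on how the shift differs between arms. The documents give neither *x* nor *r* for either arm.

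**The case against.** The best reply is that this is not the planned pathway. Several sections require eligibility first, and post-randomisation testing would occur only if a site used the fallback and Confirmation of Qualification passed the subject without a verified I2 or E2. That is right about intent, but those sections are what 10.1.2 contradicts. They show the conflict and do not remove it.

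It is also fair that few subjects should be affected, and this stands. I2 is itself defined by echocardiography, earlier diagnostic studies count if in window, and no angiogram for the Syntax score is needed without coronary disease or prior coronary intervention. I2 can be met by any of several measures, so one borderline value seldom decides it. I2 and E2 are not specific to either valve.

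Much of the reporting is already planned: disposition within each arm (SAP 7.1.1), a documented reason for early exit (Protocol 10.11), and the reason when implantation is not attempted (Protocol 10.1.3.1). An ineligible subject who is implanted anyway is a listed deviation and stays in the AT set.

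Three stronger readings are tempting and not supported:

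- From the 14- and 30-day windows a reader might infer that a large share of subjects is exposed. The windows show when a Baseline test could fall, not how many subjects would have their eligibility test then. That needs the unknown fraction using the fallback.
- A reader might infer that the route favours the sponsor's valve or uses up part of the 8-point margin. That needs losses concentrated in one arm with a risk different from the rest, and no document supports either.
- A reader might infer that the 10.1.3 review is itself a fault. It asks whether criteria are still met, which presumes earlier confirmation, and it is a legitimate check before implant.

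**Conclusion.** The point holds as an internal contradiction with a consequence for the analysis sets. As written, 10.1.2 permits the tests that establish I2 and E2 after open-label randomisation, and a subject who then fails and is not treated drops out of the sets that decide both co-primary endpoints. The ITT analysis is a sensitivity analysis only, specified for the clinical composite, and would hold little data on these subjects.

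The number affected is not given and is probably small. Neither the size nor the direction of any bias can be computed from the documents. The conclusion rests on the text leaving the route open, not on an assumed rate of exits. It is worth correcting because the correction is cheap and the conflict remains whatever the number.

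**What to change.** Reconcile 10.1.2 with 10.1.1 and 14.3.2. Either remove the last item of 10.1.2, or limit it to tests completed before randomisation. In 10.1.1, state that the randomisation system allocates an arm only once I2, and E2 where a Syntax score is required, have been recorded as confirmed.

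Leave the pre-procedure eligibility review in 10.1.3 as it is. No new recording of exits is needed beyond what the plan already collects.

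The cost is a protocol wording change and one entry check in the randomisation system. No test is added, since 10.1.1 already asks for both. The downside is that a few randomisations would wait for a TTE or Syntax result.
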